7.7.3. Adverse Event Documentation

All adverse events must be fully recorded on the adverse event eCRFs. Documentation must be supported by an entry in the subject file. Laboratory tests, vital signs and ECG abnormalities considered by the Investigator to be clinically relevant should be reported on the adverse event eCRFs. Signs and symptoms of each AE should be described in detail (e.g., start and stop dates, severity/intensity, relationship to study drug, action taken, and outcome).

Adverse events and laboratory test abnormalities fulfilling the definition of a serious adverse event should, in addition, be reported on the Serious Adverse Event Reporting Form.

7.7.4. Reporting of Serious Adverse Events

Study site personnel must alert Eli Lilly or its designee of any SAE within 24 hours of their awareness of the event via a sponsor-approved method. Alerts issued via telephone are to be immediately followed with official notification on study-specific SAE forms.

Serious adverse events occurring after a subject receive a dose of study drug will be collected until 48 hours after the dosing of the study drug, regardless of the investigator's opinion of causation. Therefore, SAEs that occur later than 48 hours after the dosing of the study drug are not required to be reported unless the investigator feels the events were related to either study drug or a protocol procedure.

If a patient experiences a SAE after signing informed consent, but prior to receiving study drug, the event will NOT be reported unless the investigator feels the event may have been caused by a protocol procedure. Previously planned (prior to signing the ICF) surgeries should not be reported as SAEs unless the underlying medical condition has worsened during the course of the study.

8. STATISTICAL ANALYSIS

8.1. General Statistical Considerations

All statistical analyses will be performed using SAS® version 8.2 or higher.

All values will be summarized by diagnostic group: cognitively normal volunteers, patients with AD, patients with MCI and where relevant, other disorders as determined by the companion protocol. Guidelines for diagnostic classification of cognitively normal volunteers, subjects with MCI and subjects with AD can be found in Appendix 11.3.

Frequency distributions including counts and percentages will be included for all categorical outcome variables. All continuous outcome variables will be summarized with statistics including mean, standard deviation, median, minimum and maximum values.

All data from the electronic case report forms (eCRFs) as well as any derived variables will be presented by listings.

Additional details concerning statistical analyses will be included in the Statistical Analysis Plan (SAP) to be completed prior to the end of enrollment into the study.

8.1.1. Populations for Analysis

The efficacy population will include all patients for whom image data are available. All analyses involving tau imaging outcomes will be based on the efficacy population. Safety

population will include all patients that received at least one dose of ¹⁸F-AV-1451 compound. Safety evaluation will be based on safety population.

8.2. Analyses

8.2.1. Efficacy Analyses

¹⁸F-AV-1451 images will be evaluated to determine if the tracer shows favorable characteristics for further development as a tau protein imaging agent. Descriptive statistics will be applied to describe the distribution of tau deposition as measured by ¹⁸F-AV-1451 across clinical diagnosis groups. Mean, standard deviation, median, minimum, and maximum values will be provided for continuous variables and counts and percentages will be provided for categorical variables

8.2.2. Safety Analyses

Adverse events including injection site reactions will be summarized in terms of number and percentage of patients experiencing an AE. The AEs will be summarized by system organ class (SOC) and preferred term using Medical Dictionary for Regulatory Activities (MedDRA) terms. Adverse events will also be presented by severity, relationship to treatment, and seriousness. All patients who experience SAEs, or who discontinue due to AEs, will be summarized.

9. USE OF DATA AND PUBLICATION

Avid adheres to the Pharmaceutical Research and Manufacturers of America (PhRMA) Principles on Conduct of Clinical Trials and Communication of Clinical Trial Results. A complete copy of these principles is available from Avid and can also be found at the PhRMA website (<http://www.phrma.org>). Our policy is briefly summarized below:

- We commit to timely communication of meaningful results of controlled clinical trials, regardless of outcome.
- As a sponsor, we may recommend that the Investigator(s) delay or decline publication in cases where the study design, conduct, or data are insufficient to allow meaningful interpretation. Avid and the Investigator(s) will discuss the study design and data in advance of the study, and again after completion, and will strive, through appropriate scientific debate, to reach a consensus regarding the potential merits of publication.
- Avid retains the right to review any manuscripts, presentations, or abstracts before they are submitted for publication. Where differences of opinion or interpretation exist regarding data planned for publication, the parties (Avid and the Investigator) should try to resolve them through appropriate scientific debate. Avid retains the right to delay publication for up to 60 days to protect intellectual property.

- Anyone who provides substantial contributions should receive appropriate recognition as an author or contributor when the manuscript is published.

This is a multi-center study. A multi-center publication, reporting the primary analysis data set, should precede any other publications.

10. INVESTIGATOR'S REGULATORY OBLIGATIONS

All clinical work conducted under this protocol is subject to Good Clinical Practice regulations; this may include an inspection by Avid and/or Health Authority representatives (FDA or international regulatory authorities) at any time.

10.1. Institutional Review Board (IRB)

The intent of the research program, the trial protocol, the patient information/informed consent form and any advertising material used to recruit subjects must be submitted to the clinical investigator's local IRB and its approval must be obtained prior to its use. A copy of the approval must be forwarded to Avid. When necessary, an extension or renewal of IRB approval must be obtained and also forwarded to Avid.

10.2. Informed Consent

A signed, written informed consent must be obtained from each patient. A copy of the signed informed consent should be given to the patient for their records. A copy of the local IRB's approved version of the informed consent form must be forwarded to Avid, or designee, for review prior to being used to obtain patient consent.

10.3. Protocol Adherence

The protocol must be read thoroughly and the instructions must be followed exactly. Where a deviation occurs, it must be documented, the sponsor/monitor informed, and a course of action agreed upon.

10.4. Documents Necessary for Initiation of the Trial

Avid must be provided with the following documents prior to the enrollment of any subjects:

- Original signed and dated Statement of Agreement page;
- Copy of the IRB and radiation safety committee approval (if applicable);
- Copy of the IRB stamped approved consent form;
- Name and location of the laboratory utilized for laboratory assays, and other facilities conducting tests, including laboratory certification number and date of certification if available. Avid may be responsible for supplying these to the investigator if a central laboratory is used;
- List of reference range laboratory values. Avid may be responsible for this if a central laboratory is used; and

- Any additional licenses required in order to order to use ^{18}F -AV-1451.

10.5. Study Drug Control

The receipt of clinical supplies must be documented at the site.

All drug supplies for this trial should be retained in a safe and secure place at all times during the trial. ^{18}F -AV-1451 Injection should be prepared by a qualified PET manufacturing site and administered by a qualified individual under the investigator's supervision. All drug supplies must be accounted for. After completion of the trial, all remaining clinical supplies must be returned to the sponsor or their representative.

10.6. Data Collection

Electronic case report forms (eCRFs) will be used for this trial. Individual patient files should include appropriate source documents, including but not limited to patient's medical records and laboratory test results. The files should include information such as visit dates, records of medical history, examinations administered, laboratory, concomitant treatment, any adverse event encountered and other notes as appropriate. These constitute "source data". All entries on the eCRFs must be backed up by source data. Original electronic versions of imaging studies are also considered source data and should be kept on file by the site/imaging center, and appropriate copies should be forwarded to Avid, or a designated Imaging Core Lab, as specified in the Imaging Manual.

Each patient's source file should include an original signed informed consent form. When the trial is completed, the informed consent form should be kept on file with other trial related records.

All original laboratory reports must be available for review in each patient's file. It is important that the original reports be available for review because of the possibility of inaccuracies or errors in transcribing data from original records to the eCRF.

The eCRFs must be kept in order and up-to-date so that they always reflect the latest observations on the subjects that are enrolled in the trial. The eCRFs must be completed for each patient enrolled in the trial and signed by the investigator. This should be done as soon as possible after completion of the patient's participation in the trial. A monitor will verify the source data for all information on the eCRF.

10.7. Adverse Events

All adverse events encountered during the clinical trial must be documented on the eCRF, whether or not considered drug-related.

Eli Lilly must be notified immediately (as soon as possible, and in all cases within 24 hours) of a drug experience, condition, development, or event, which is considered serious. Eli Lilly must be notified immediately of any findings with the use of the drug that may suggest significant hazards, contraindications, adverse drug reactions (ADRs) and precautions pertinent to the safety of the drug. The investigator will be requested to

complete a separate report form in addition to the information on the eCRF. See section 7.7.4 for reporting serious adverse events.

If a SAE is determined to be unexpected (not previously reported or described by Avid), and study drug-related, Eli Lilly will notify the investigator in writing. The investigator should forward this notification to the IRB within 24 hours of receipt.

10.8. Records Retention

All correspondence (e.g., with Avid, IRB, etc.) relating to this clinical trial should be kept in appropriate file folders. Records of subjects, source documents, and drug inventory sheets pertaining to the trial must be kept on file. Records must be retained until the date a marketing application (NDA) is approved for the drug for the indication for which it is being investigated, or until 2 years following the date of clinical trial termination or completion, whichever is later. If no application is to be filed or if the application is not approved for such indication, records should be kept until 2 years following the date of clinical trial termination, or completion.

If an investigator moves, withdraws from an investigation, or retires, the responsibility for maintaining the records may be transferred to another person who will accept the responsibility. Notice of transfer must be made to and agreed upon by Avid.

11.2. Trial Flow Chart

Evaluations	Screen	Pre-dose	Dose	PET Imaging	End of Imaging	2 – 3 days post injection	
Signed Consent	X						
Medical / Disease History	X						
Concomitant Meds	X	X					
ECG	X						
MMSE	X						
Physician Visit	X	X				X	
OSU TBI-ID	X						
Vital Signs ²		X				X	
Pregnancy Test	X	X					
¹⁸ F-AV-1451 Administration			X				
PET Imaging ¹				Continuous 20 minute scan			
Follow-up Phone Call						X	
Adverse Event Assessment	X	X	X	X	X	X	

¹Sites may elect to perform additional imaging time points with prior sponsor approval.

²Height and weight will be measured prior to injection on imaging day.

11.3. Guidelines for diagnostic classification

Subjects meeting the NINCDS-ADRDA criteria (McKhann 2011) should be classified as possible or probable AD:

1. Patients with dementia as evidenced by a MMSE score typically ranging from 10 to 24, boundaries included, at screening;
2. Patients whose history of cognitive decline has been gradual in onset and progressive over months to years. Evidence should be present indicating sustained memory deterioration in an otherwise cognitively normal patient, plus additional cognitive deficits in another cognitive function such as: learning, language presentation, visuospatial presentation, and executive dysfunction.

Subjects who meet the following NIA-Alzheimer's Association working group's diagnostic guidelines for AD: Alzheimer's Dementia 7:270-9, 2011 (Albert 2011), criteria should be classified as mild cognitive impairment:

1. Have cognitive decline verified by the study physician.
2. Evidence of objective impairment in one or more cognitive domains, with supporting evidence from objective testing if available.
3. Preservation of independence in functional abilities.
4. Not demented.
5. Patients typically with an MMSE score ≥ 24 .

Subjects who meet the following criteria should be classified as cognitively normal volunteers:

1. Subjects with an MMSE score ≥ 29 , and are cognitively normal based on history (no evidence of significant recent cognitive decline) and psychometric test battery at screening;

Note: Subjects with dementia who do not meet criteria for probable AD, as described in point number 1, should be classified as 'other dementing disorders'.

INVESTIGATOR'S AGREEMENT TO PROTOCOL

Protocol ¹⁸F-AV-1451-A14: "Clinical Evaluation of ¹⁸F-AV-1451"

Date and Version: 05Sep2014 Amendment 1

I agree to conduct the study according to this protocol and to comply with its obligations, subject to ethical and safety considerations and all applicable regulations (ICH, CFR).

I shall not disclose the confidential information contained in this protocol or any results obtained from the study, except for publication in accordance with Section 9 of this protocol, without written authorization from Avid.

Printed Name

Date

Signature

1 LIST OF ABBREVIATIONS AND DEFINITIONS OF TERMS

Table 1: Abbreviations

AAL	Automated anatomical labeling
Amyloid beta	A β
AD	Alzheimer's disease
AE	adverse event
ANCOVA	Analysis of covariance
CFB	change from baseline
C.I.	Confidence interval
CI	cognitively impaired
CN	cognitively normal
CRF	Case report form
CSF	cerebrospinal fluid
CSR	clinical study report
DBP	diastolic blood pressure
ECG	electrocardiogram
IV	intravenous
LSM	Least squares mean
Max	maximum
MBq	Megabecquerel
mCi	Millicurie
MedDRA	Medical Dictionary for Regulatory Activities
Min	minimum
MMSE	Mini-Mental State Examination
MUBADA	Multiblock Barycentric Discriminant Analysis
N	Sample size
ODD	Other Dementing Disease
OND	Other Neurological Disorder
OSU-TBI	Ohio State University – Traumatic Brain Injury
PCS	Potential clinically significant
PD	Psychiatric Disorder
PERSI	parametric estimated signal reference intensity
PET	positron emission tomography
PLT	Posterolateral Temporal
PR	Pulse rate
PT	preferred term
RR	Respiratory rate
SAE	Serious adverse event
SAP	statistical analysis plan
SAS	Statistical Analysis Software
SBP	Systolic blood pressure
SD	Standard deviation

SE	Standard error
SOC	system organ class
SUV _r	standardized uptake value ratio
TEAE	treatment-emergent adverse event
WHO	World Health Organization

2 INTRODUCTION

¹⁸F-AV-1451 (originally named [F-18]T807 by Siemens Molecular Imaging Biomarker Research group) has been developed as a positron emitting radiopharmaceutical for *in vivo* imaging of tau protein aggregates (Xia et al., 2013). Autoradiography results using tissue sections from human brains showed a strong signal in the grey matter of cortical slices from tau positive brains but weak or no binding in tau negative, amyloid-beta (A β) positive, or tau and A β negative tissue

AV-1451 was assessed in competitive binding assays against a panel of 72 of the most common central nervous system (CNS) targets and no clinically relevant inhibition was seen. AV-1451 was positive in the *in vitro* hERG assay, albeit at a concentration more than 40-fold the maximum theoretical AV-1451 plasma concentration. Additionally, *in vivo* cardiovascular safety pharmacology assessments in dogs showed no evidence of QT prolongation at doses up to 50x the intended maximum human dose (MHD). Nonetheless, until sufficient human cardiovascular safety data are available, initial clinical studies will exclude subjects with a history of risk factors for Torsades de Pointes and subjects taking drugs known to prolong the QT interval.

In vivo safety pharmacology studies were also conducted in rats to determine potential effects on the CNS and respiratory systems. In these studies no clinically relevant effects were reported at doses exceeding 100x the intended MHD. Additionally, non-radioactive AV-1451 has been tested in single and repeat dose toxicology studies in rat and dog species. In each of these studies the no observable adverse effect levels (NOAELs) were the highest doses tested (150x MHD for single, 50x MHD for repeat).

Potential genotoxicity of non-radioactive AV-1451 was tested in both *in vitro* and *in vivo* assays. In the *in vitro* assays, AV-1451 tested positive for potential genotoxicity. However, in the *in vivo* rat micronucleus assay at doses up to 750x MHD (scaled allometrically), AV-1451 showed no evidence of genotoxicity. The different results in the *in vitro* genotoxicity assays and the *in vivo* micronucleus study are likely related to differences in the exposure conditions encountered by the target cells in the different test systems. *In vivo*, AV-1451 is cleared rapidly; however, the *in vitro* experiments employ static, prolonged exposure of cells to high concentrations of the test article. While the *in vitro* data show the potential for genotoxicity, the *in vivo* data provide assurance that genotoxicity is unlikely to occur at clinically-relevant doses for human diagnostic studies.

Human dosimetry has been obtained in nine subjects. Generally, the radiotracer distribution was consistent among the subjects and showed rapid hepatobiliary clearance. There were three organs that received estimated doses higher than 0.05 mSv/MBq. The organ that received the largest estimated dose was the upper large intestinal wall (0.0962 ± 0.0134 mSv/MBq), followed by the small intestine and the liver. The Effective Dose was 0.0241 ± 0.0016 mSv/MBq. This results in an estimated Effective Dose of 8.92 mSv for an anticipated 370 MBq (10 mCi) injection and is comparable to the effective dose of approved ¹⁸F-labeled compounds such as fluorodeoxyglucose (FDG) and florbetapir F 18 injection.

The present study is designed to expand the database of ¹⁸F-AV-1451 safety and tau binding as measured by PET imaging, and to provide standardized conditions for tau use, data collection, and analysis to facilitate companion studies including, but not limited to, longitudinal studies of aging, depression, and traumatic brain injury.

The purpose of this statistical analysis plan (SAP) is to describe the statistical analyses for study ¹⁸F-AV-1451-A14. This SAP should be read in conjunction with the A14 protocol.

3 STUDY OBJECTIVES

The primary objectives of this study are:

- to provide standardized conditions for flortaucipir use, data collection, and analysis to facilitate evaluation of subjects' tau burden.
- To expand the flortaucipir safety database.

4 STUDY DESIGN

4.1 General Design

This is a phase II, multicenter study that will expand the flortaucipir safety database and explore tau binding as measured by PET imaging, and will provide standardized conditions for the use, data collection and analysis of flortaucipir to facilitate companion studies looking at tauopathies.

4.1.1 Screening Visit

Screening assessment may have taken place over several days and included collection of demographic information, medical assessment for eligibility, electrocardiogram (ECG), a brief cognitive assessment (i.e. Mini-mental State Exam [MMSE]), and a traumatic brain injury questionnaire (i.e. Ohio State University Traumatic Brain Injury [OSU-TBI]).

4.1.2 Flortaucipir PET Imaging Visit

For the flortaucipir PET imaging session, an intravenous (IV) catheter was placed for administration of flortaucipir injection. Subjects received a single IV bolus injection target dose of 240 megabecquerel (MBq) (6.49 millicuries (mCi)) or 370 MBq (10 mCi) of flortaucipir injection. Vital signs were taken in a supine position immediately prior to (within 30 minutes of) flortaucipir injection and at the completion of imaging prior to subject discharge. At approximately 80 minutes post injection, a 20-minute dynamic brain scan was obtained. Sites may have elected to use an alternative imaging protocol (i.e. different scan duration or scan start time) with additional time points with sponsor approval. All datasets were submitted to the sponsor for analysis.

Adverse events (AE) were continuously monitored during the imaging visit (see section 6.6.2). Any subject who experienced an adverse event was not discharged until the event had resolved or stabilized.

4.1.3 Follow-Up Phone Call

A follow-up phone call to the subject, or designated decision maker, was conducted between 2 and 3 business days after imaging day, but not before 48 hours post-injection, to confirm subject well-being and to collect information about any new adverse events. If both of these days were not business days, the follow-up phone call occurred the following business day.

4.1.4 Repeat Imaging

Longitudinal imaging studies may have been conducted under protocol ¹⁸F-AV-1451-A14 with prior sponsor approval. In these studies, subjects may have had up to two imaging sessions within a 12-month time-frame. If the second scan was obtained more than 3 months after the previous scan, then the MMSE was repeated and updated OSU-TBI, medical history, and concomitant medications information was collected. Procedures for each the repeat imaging were identical to those described above.

4.2 Method of Assignment of Subjects to Treatment and Diagnosis Groups

Subjects who qualified for the study received a single IV bolus injection with a target dose of 240 (6.49 mCi) or 370 MBq (10 mCi) of flortaucipir (¹⁸F) injection.

Subjects will be classified into diagnosis groups (Alzheimer’s disease AD [AD], mild cognitive impairment [MCI], control subject [CN], other dementing disorder [ODD], other neurological disorder [OND], psychiatric disorder [PD]) as outlined by pre-specified criteria (see protocol amendment 1, appendix 11.3 for details), however there was no design (adaptive or otherwise) to stratify an equal number of subjects in each diagnosis group. Diagnosis groups will be consolidated in the following way in the result summaries.

Table 2: Consolidation of Diagnosis Groups for Presentation of Results

Diagnosis Group	Presentation Group
AD	Cognitively Impaired (CI)
MCI	
ODD	
OND	
PD	
CN	Cognitively Normal (CN)

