8.4 Analysis of Efficacy Parameters

8.4.1 Analysis of Primary Efficacy Variable

8.4.1.1 Quantitative Assessment of Images

The MUBADA SUV_r (as described in section 6.4.1.1) from the available imaging visits will be summarized using descriptive statistics (n, mean, SD, min, max, and median) for the efficacy population by cognitive groups (CI and CN). An analysis of covariance (ANCOVA) model will be used to test significant differences in baseline MUBADA SUV_r between the two cognitive groups adjusted for age. All descriptive statistics, including LSM (+/- SE), LSM differences (95% C.I.), and p-values will be reported in a table.

MUBADA SUV_r will also be presented in a scatter plot by clinical group.

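### The SAP tabulates tau SUVr only as CI versus CN, so the by-diagnosis statistics that the protocol promises, for AD and MCI in particular, are not produced

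*SAP*

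**What the plan says.** **Protocol.** Section 8.1 sets the grouping for every summary: "All values will be summarized by diagnostic group: cognitively normal volunteers, patients with AD, patients with MCI", and then "where relevant, other disorders as determined by the companion protocol". Section 8.2.1 applies this to the imaging outcome. It promises the distribution of tau "across clinical diagnosis groups" and names the statistics: "Mean, standard deviation, median, minimum, and maximum values will be provided for continuous variables". The Statistical Methods entry of the synopsis makes the same commitment. On classification, section 8.1 says: "Guidelines for diagnostic classification of cognitively normal volunteers, subjects with MCI and subjects with AD can be found in Appendix 11.3".

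**SAP.** Section 4.2 lists six diagnosis groups: AD, MCI, CN, other dementing disorder (ODD), other neurological disorder (OND) and psychiatric disorder (PD). It refers to protocol Appendix 11.3 for the criteria and adds: "Diagnosis groups will be consolidated in the following way in the result summaries". Table 2 maps five of the six to CI and leaves CN alone. Section 8.4.1.1 then summarises MUBADA SUVr "for the efficacy population by cognitive groups (CI and CN", and compares the same two groups by ANCOVA adjusted for age. It adds that SUVr "will also be presented in a scatter plot by clinical group". Section 7.6 rules out subgroup analysis. Section 5, whose heading covers changes to planned analyses, mentions none.

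**The concern.** The protocol's only stated efficacy output is a description of tau by diagnosis. The SAP's job is to add detail to that output, but it replaces the grouping with a coarser one. A reader of the study report could not learn the mean or spread of SUVr in AD or in MCI from any planned table.

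The one between-group result that remains is also hard to interpret. The CI mean is a weighted average over the diagnoses that the companion studies happened to enrol, and SAP 4.2 says that the design made no attempt to balance the groups. The same CI versus CN difference could come from a large excess in a few AD subjects or a modest excess in everyone.

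A secondary question is whether the CI label fits all five groups, since the appendix cited for the criteria does not cover OND or PD.

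**Working it through.** The plan states no figure to reproduce: SAP 4.4 gives no power or sample size calculation. The check compares the texts and adds a short illustration.

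**Step 1: what is promised and what is planned.**

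- Named without condition in protocol 8.1: CN, AD, MCI (3 groups). Other disorders are conditional on relevance.
- Given their own SUVr statistics in SAP 8.4.1.1: CN only. AD and MCI fall within CI.
- Unconditional shortfall: 2 of 3 named groups. With the five statistics listed in protocol 8.2.1, that is 2 × 5 = 10 promised summary values missing. Any relevant other disorders add to this.

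Four cells of Table 2 are empty in the extracted text. I read them as one merged CI cell, which agrees with the two cognitive groups of 8.4.1.1.

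**Step 2: does another planned output fill the gap?**

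- The MMSE–SUVr Spearman correlation (SAP 8.4.1.2) has no breakdown by diagnosis.
- The scatter plot may show individual diagnoses, but its grouping term is not defined, and a plot reports no mean or SD.
- The vital signs table (SAP 8.5.3) is by diagnosis groups but holds no tau data.
- The CI row reports n, mean, SD, median, minimum and maximum, and the ANCOVA adds a least squares mean with SE. All of these describe the pool.

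**Step 3: can the pooled row stand in?** With weights w_k and group means m_k, measured as excess over CN in within-group SD units:

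- CI mean = Σ w_k m_k
- CI variance = 1 + Σ w_k m_k² − (Σ w_k m_k)²

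The values below are assumed, are not in the documents, and ignore the age adjustment.

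- Mix A: AD 20% at 1.0, MCI 20% at 0.5, the other three together 60% at 0. Mean = 0.2 × 1.0 + 0.2 × 0.5 + 0.6 × 0 = 0.30. Variance = 1 + (0.2 × 1.00 + 0.2 × 0.25) − 0.30² = 1.16, so SD = 1.08.
- Mix B: every group at 0.30. Mean = 0.30. Variance = 1 + 0.09 − 0.09 = 1, so SD = 1.00.

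The difference from CN is identical and the SDs are close, yet tau by diagnosis is quite different. This shows only that a pooled mean does not identify its parts. It says nothing about what this study will find.

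**Step 4: the label.** Appendix 11.3 gives criteria for AD, MCI and CN, and a closing note assigns remaining dementia cases to other dementing disorders. It has nothing for OND or PD, so 2 of the 6 groups for which SAP 4.2 cites it are not covered.

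**The case against.** The strongest replies are these.

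- **The SAP is to be read with the protocol, so the by-diagnosis table is still owed.** SAP section 2 does say the two belong together. But the 4.2 sentence expressly governs the result summaries and 8.4.1.1 names the two groups, so a programmer following the SAP would not produce the table.
- **The scatter plot probably shows the diagnoses.** This is a fair reading: 8.4.1.1 uses one term for the table and another for the plot, and the second is close to the protocol's wording. If so, tau by diagnosis is displayed, but still without the promised statistics.
- **No data are lost and no decision depends on this.** Both are true. Protocol 8.1 also promises listings of derived variables, from which the table could be rebuilt. This limits the severity but does not meet a commitment to summary statistics.
- **Other disorders are left to the companion protocols.** This stands. A reader might infer that the protocol requires a separate row for each of the five pooled groups. It does not: beyond AD and MCI, the promise holds only where relevant.

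A reader might also infer that OND and PD subjects are wrongly labelled as impaired. The documents do not show that. Protocol 8.1 hands other disorders to companion protocols that were not available for review, and those may require impairment. What can be said is that the label has no support in these two documents.

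**Conclusion.** The point holds as a reporting and interpretation defect that should be fixed. AD and MCI, 2 of the 3 groups the protocol names outright, get no SUVr statistics of their own, nor do any relevant other disorders, and the SAP does not declare the change. This conclusion rests on the text, plus the reading of Table 2 as one merged CI cell.

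It is tempting to go further and say that pooling dilutes the CI versus CN contrast or costs it power. The documents do not support that: they give no numbers by diagnosis and no SUVr values, so the size and direction of any effect are unknown. SAP 4.4 also states that the objectives carry no hypothesis, so no decision rule is at risk. The label question is secondary and amounts to absence of support.

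**What to change.** 1. In SAP 8.4.1.1, add a MUBADA SUVr descriptive table (n, mean, SD, median, minimum, maximum) for CN, AD and MCI, and for ODD, OND and PD where present.
2. Amend the consolidation sentence in SAP 4.2 so that Table 2 does not apply to this table. Add to SAP 7.6 that the table is descriptive and is not a subgroup analysis. Without both changes the SAP would contradict itself.
3. Define 'clinical group' in the scatter plot as these diagnosis groups.
4. Declare in SAP section 5 any departure from protocol 8.1 and 8.2.1 that remains.
5. Secondary: correct the Appendix 11.3 reference for OND and PD. If the companion protocols require impairment for those groups, cite their criteria; if not, give the pool a neutral label such as non-control.

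The CI versus CN ANCOVA can stay.

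The cost is one table and a few sentences, with no new data and no new test. The downside is that some rows may be small. The 95% half-width of a group mean, in SD units, is t(0.975, n − 1)/√n: 1.24, 0.72, 0.47 and 0.32 at assumed sizes of 5, 10, 20 and 40. Small rows must be read as description only.
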